This will be a randomized, open-label clinical trial. Veteran opioid dependent men and women will be randomized to one of two treatment groups: low dose range of BUP/NLX (Less than or equal to 8mg) vs. high dose range of BUP/NLX (Greater than or equal to 16mg). During induction into buprenorphine, all participants will be started at a dose of 2mg, and this dose will be increased as needed for stabilization of opioid withdrawal symptoms, up to 8mg for the low dose group, and up to at least 16mg for the high dose group, within about 7 day period. If a participant is randomized to the low dose group but is experiencing withdrawal symptoms that cannot be stabilized the participant will be discharged from the study. Participants will be clinically managed and will get monthly assessments. Participants will be seen on a daily basis (excluding weekends) for the initial 7 day induction. Once subjects are on maintenance dose of BUP/NLX (goal is within 5 days), they will be seen weekly by study RN for medical management, symptom evaluation, and medication refill. Participants will also complete study questionnaires at this time. At the end of the 12-week study, participants will either be referred to a buprenorphine clinic if they wish to continue this medication, or if they wish to be drug free, will undergo detoxification from BUP/NLX for up to a 4-week period. Follow-up visits, scheduled at 1, 3, and 6 months after study completion, will evaluate the durability of treatment effects on drug use and psychosocial outcomes.

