Use of other drugs of abuse and program termination: At every clinic visit, the subjects will be asked to take a breathalyzer test as a measure of the blood alcohol levels. Subjects will be asked not to use alcohol throughout the study since alcohol may interact with BUP/NLX causing CNS toxicity and respiratory depression. If a breathalyzer reading is 0.04 or greater, the buprenorphine dose will be held until the breathalyzer reading falls below 0.04. If the breathalyzer levels do not fall below 0.04 until the dispensing hours end, subjects will not receive BUP/NLX for that day. If the reading is between 0.01 – 0.04, the subject will receive one-half of their BUP/NLX dose. If the level falls below 0.01 prior to close of dispensing that day, the subject can receive a full dose. If the breathalyzer reading is over the legal limit, 0.08 or more, the study physician will be notified. If the study physician determines that it is unsafe for the participant to leave the clinic, the participant may be taken to the Psychiatric Emergency Room for further evaluation and treatment.

During the final phase of the study, we estimate that approximately 20% of participants will opt for detoxification. In those cases, we will provide a detoxification or a two to four-week taper from buprenorphine depending on each individual's needs. Subjects will then be referred to appropriate outpatient substance abuse treatment (abstinence based). The rest of the subjects will likely request to continue on buprenorphine maintenance. We will refer those patients to the VA clinic.

At any point in the study, subjects will be withdrawn if they regularly miss medications (2 weeks in a row). Subjects may also be withdrawn from the program if urine toxicology screens show frequent use of benzodiazepines or barbiturates. Subjects withdrawn from the study will be offered detoxification from buprenorphine, possibly for naltrexone treatment or referral to methadone maintenance. Subjects will also be withdrawn from the study if the investigator has evidence that subjects' health or well-being may be threatened by continuation in the study. Should a pregnancy test become positive, the subject will be withdrawn from the study and referred to an appropriate treatment program.

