9. SAFTEE
10. SCID for DSM-V for diagnostic clarification of psychiatric and substance use dependence will be completed in an appropriate time period depending on patient's presenting symptoms.
11. Time Line Followback (TLFB)
12. Urine toxicology screening for drugs of abuse (i.e., cannabinoids, opiates, amphetamine, cocaine)
13. Vital signs (blood pressure, heart rate, weight)

The following measures will be completed weekly during study participation. The duration of the weekly assessments will be approximately 45 minutes.

1. Brief Pain Inventory-Short Form
2. Center for Epidemiologic Studies Depression (CES-D) scale Clinical Opiate Withdrawal Scale
3. Columbia-Suicide Severity Rating Scale (C-SSRS)
4. Drug Use Inventory
5. Post Traumatic Stress Disorder Checklist (PCL-C)

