6. SAFTEE
7. Time Line Followback (TLFB)
8. Breathalyzer [additional assessment will be done if suspect alcohol use].
9. Urine Toxicology Screening for drugs of abuse (i.e., cannabinoids, opiates, amphetamine, cocaine)
10. Vital signs (blood pressure, heart rate)
11. Weight

The following measures will be completed at 1, 3 and 6 month follow-up:

1. Brief Pain Inventory-Short Form
2. Center for Epidemiologic Studies Depression (CES-D) scale
3. Clinical Opiate Withdrawal Scale
4. Drug Use Inventory
5. Time Line Followback (TLFB)
6. Urine Toxicology Screening for drugs of abuse

For women of childbearing age, a urine pregnancy test will be done at screening, and monthly during study participation.

A. Laboratory Tests and Vital Signs:

- Blood chemistries (chem 19 + GGT, CBC with differential, Thyroid functions, Urinalysis and urine toxicology) and EKG as well as a general physical examination will be performed at intake. Additionally blood chemistries will be taken at week 12.
- Urinalyses: Urines will be analyzed for the presence of drugs of abuse (including opioids, amphetamines, cocaine metabolite and marijuana) on a weekly basis. Breath analysis for alcohol will be performed on a regular basis, although current alcohol physical dependence is among the exclusion criteria.

- Vital signs including blood pressure, heart rate, and weight will be collected each week.
- B. Psychosocial Assessments: A set of instruments will provide general patient information, including demographic data, substance use history, previous substance use and psychiatric treatment history, medical history and family substance abuse history. Assessments include:
 - Brief Pain Inventory – Short Form: BPI-SF is a self-report questionnaire that assesses severity of pain, impact of pain on daily function, location of pain, pain medications and amount of pain relief in the past 24 hours or the past week (Cleeland and Ryan, 1994).

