- C. SAFTEE: The SAFTEE is a technique for the systematic assessment of side effects in clinical trials. The SAFTEE will be reviewed by the study nurse and specific symptoms, as well as severity, will be recorded. The SAFTEE will be administered weekly.

Data Analysis Methods:

A. Sample Size and Power Analysis:

For this pilot study, we will recruit a total of 200 subjects, 100 subjects in each treatment arm. No previous studies have examined the influence of BUP/NLX dose on treatment outcomes in prescription-opioid dependent individuals. Our sample of 200 will require an effect size of .25 to detect differences between the two treatment groups for the number of opioid positive urines during the treatment period.

B. Statistical analysis:

The principal analyses will be done on the modified intention to treat sample, that is, subjects receiving at least one dose of BUP/NLX. First, we will determine the success of the randomization by comparing the two treatment groups on socio-demographic and baseline clinical characteristics using chi-square for categorical variables and ANOVA for continuous variables. Second, survival analysis will be used to determine differences between experimental groups in treatment retention. Third, random regression analyses (HLM), (Hedeker and Gibbons 1996) will be conducted to examine if the change in opioid use behavior over time varies as a function of the treatment factors.

Risks and Benefits:

Potential risks

1. Buprenorphine: Buprenorphine, formulated as a sublingual tablet, is available alone or in combination tablet containing buprenorphine and naloxone in a ratio of 4:1. The doses of buprenorphine/naloxone used here are within the recommended guidelines of the manufacturer (4-24 mg/day). In this study, combination tablet will be used, since it is less likely to be diverted than the buprenorphine alone formulation. Common side effects of buprenorphine/naloxone include abdominal pain, constipation, nausea, vomiting, headache sweating, sedation, and allergic reaction. Uncommon but more serious adverse effects of buprenorphine/naloxone include hepatic abnormalities, orthostatic hypotension and respiratory depression.
2. Buprenorphine/Naloxone detoxification: Detoxification from buprenorphine/naloxone can produce signs and symptoms of opiate withdrawal, including nasal congestion, abdominal symptoms, anxiety, myalgia, insomnia, sweating, and diarrhea.

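### Low-dose participants who cannot be stabilized leave the study, not just the drug, and no weekly urines are provided for afterwards, so opioid-use data are lost from one arm; a missed-medication rule does the same in both arms

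*Combined protocol and SAP*

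**What the plan says.** Two rules take people out of the trial.

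- **Low-dose arm only.** Under Research Plan, if someone in the low-dose group is "experiencing withdrawal symptoms that cannot be stabilized the participant will be discharged from the study". No such exit is stated for the high-dose group.
- **Both arms.** Under Use of other drugs of abuse and program termination, "subjects will be withdrawn if they regularly miss medications (2 weeks in a row". That sentence does not say withdrawn from what. The sentences after it do: they speak of withdrawal from the study, and offer detoxification from buprenorphine to those withdrawn.

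Under Assessments, the weekly list opens with "The following measures will be completed weekly during study participation" and includes TLFB and "Urine Toxicology Screening for drugs of abuse". The only later collection is at "Follow-up visits, scheduled at 1, 3, and 6 months after study completion". The text does not say whether people who left early attend those visits.

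Under Data Analysis Methods, "The principal analyses will be done on the modified intention to treat sample", defined as those who received at least one dose. The sizing sentence uses the "number of opioid positive urines during the treatment period". Opioid use is analysed by random regression (HLM), which "will be conducted to examine if the change in opioid use behavior over time varies as a function of the treatment factors". No rule for missing urines is given.

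**The concern.** The plan keeps these people in the principal analysis but makes no provision for measuring their opioid use for the rest of the 12 weeks. What removes them is unlikely to be unrelated to outcome. A low-dose participant who cannot be stabilized is likely to be someone for whom the low dose has failed, and that is what the trial sets out to compare. If such people go on to use opioids, the use is not recorded, and it goes unrecorded in the low-dose arm alone.

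HLM uses every available urine and tolerates missing weeks that the modelled data explain. The model described has treatment and time, with other formal treatment as a covariate (Medication Compliance). It includes neither failure to stabilize nor missed medication, which are the two triggers. A raw count of positive urines is more exposed, because weeks never collected add nothing to it.

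**Working it through.** **The plan's own figure.** Section A gives an effect size of .25 for 200 people, without alpha, power or metric, so it cannot be reproduced uniquely. With 100 per arm and two-sided 5%, power is Φ(d√50 − 1.96). That is 42% if .25 is a standardized difference, and 94% if it is Cohen's f (d = 0.50). The point here does not depend on it; .25 SD serves only as a yardstick. The SD of the count of 12 urines is √(12pq(1+11r)). Assuming p = 0.3, r = 0.2 it is 2.84; assuming p = 0.5, r = 0.5 it is 4.42. So .25 SD is about 0.71 to 1.10 urines.

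**Low-dose discharge: data lost.** Inputs from the plan are 100 per arm and 12 weekly urines, so 1,200 per arm. Discharge is assumed after week 1, because stabilization is planned within about 7 days. Each 10 people discharged lose 10 × 11 = 110 urines, and 110/1,200 = 9.2% of the arm. Ten is a unit, not an estimate.

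**Low-dose discharge: illustrative effect.** Assume 30% of urines are positive on treatment and a share *s* after discharge, with *s* between 30% and 80%. Neither figure is in the documents. For 10 of 100 discharged:

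- True arm mean: 12 × 0.3 + 0.10 × 11 × (*s* − 0.3) = 3.60 (*s* = 0.3) to 4.15 (*s* = 0.8).
- Count from collected urines: 3.60 − 0.10 × 11 × 0.3 = 3.27. This is too low by 0.33 to 0.88.
- A model that projects the on-study 30% into the missing weeks gives 3.60. This is too low by 0.00 to 0.55. If discharged people were already mostly positive in week 1, HLM would recover part of this.

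The high-dose arm has no matching loss from this rule, so the shortfall passes straight into the between-arm difference and flatters the low dose.

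**Missed-medication rule: data lost.** The trigger is not defined, so I took three readings.

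*Two missed weekly pick-ups.* No attending participant is withdrawn, and the only urines lost are from people who would have come back. Assume 30–50% lapse, 10–30% of them would return, and 4.5 of 12 weeks are lost. The loss is then 0.30 × 0.10 × 0.375 = 1.1% to 0.50 × 0.30 × 0.375 = 5.6%.

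*At least k missed days in each of two consecutive weeks*, with days independent. The weekly trigger is P(at least k of 7 days missed), binomial. P(two trigger weeks running within 12) follows by recursion, and urines lost are Σ P(withdrawn at week t) × (12 − t)/12.

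| Missed days (assumed) | k = 2: withdrawn | k = 2: urines lost | k = 3: withdrawn | k = 3: urines lost |
|---|---|---|---|---|
| 5% | 2.1% | 0.9% | 0.02% | 0.01% |
| 10% | 20.0% | 8.7% | 0.7% | 0.3% |
| 20% | 81.5% | 44.8% | 19.6% | 8.6% |

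**Missed-medication rule: effect on one arm's estimate.** I simulated 300,000 people in one arm, with missed days varying between people (mean 10%). The fit was by maximum likelihood on the available urines, using an unstructured normal model as a stand-in for HLM.

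| Assumption | k = 2: shift in positivity | k = 3: shift in positivity |
|---|---|---|
| Adherence unrelated to use | none | none |
| Correlation 0.5 | 1.3 points low (0.16 of 12 urines) | about 0.4 points low |
| Correlation 0.5, use rises 20 points after withdrawal | 4.0 points low (0.48 urines) | about 1.2 points low |

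At k = 2 about 25% are withdrawn and 14% of urines lost; at k = 3 about 7% and 4%. These are shifts within one arm. They cancel in the comparison if the arms are alike.

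**The case against.** The strongest reply is that the missed-medication rule does no demonstrated harm to the question the trial asks. It reads the same in both arms, and nothing in the documents suggests that missed doses will differ by dose. The planned analysis concerns a treatment-by-time contrast, whereas the simulation reports a level in one arm. Medication is issued weekly and goes back to the pharmacy if the person does not attend, so two missed pick-ups is a plausible reading, and on it little is lost. All of this stands. A reader might infer from the 82% and 45% extremes, or from the per-arm shifts, that this rule distorts the dose comparison. The documents do not support that inference: the threshold and the rates are assumed.

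A reader might also infer that the result could change sign. With 40% against 20% withdrawn after week 4, and positivity rising from 30% to 80%, raw counts differ by −0.48 where the truth is +0.80. But those rates are invented, raw counts are not the planned HLM, and equal withdrawal gives no difference at all.

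Two more limits stand. No sentence forbids collection after exit; that it stops is inferred from the schedule. And retention, the first main outcome named under Purpose, is analysed by survival methods in which leaving is the event, so it is not harmed in the same way.

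The reply does not reach the low-dose discharge. That rule applies to one arm by its own wording, and its trigger is failure of the assigned dose. The 1-, 3- and 6-month visits do not repair it, because they do not supply the weekly treatment-period series even if discharged people attend.

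**Conclusion.** The concern holds, led by the low-dose discharge. As written, the plan loses treatment-period opioid data for reasons related to outcome while keeping the people concerned in the principal analysis. The low-dose discharge can bias the dose comparison, most plausibly by understating opioid use on the low dose. Each 10 discharges after week 1 remove 9.2% of that arm's urines. Under the assumed positivity rates they understate the arm mean by 0 to 0.55 urines in a model-based analysis, or 0.33 to 0.88 in a raw count, against 0.7 to 1.1 urines for .25 SD. The discharge rate, its timing and later use are not in the documents, so the actual bias is unknown.

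The missed-medication rule adds a loss in both arms that runs from negligible to large with its undefined trigger. No between-arm bias from it is shown. The change is worth making because it is specific and cheap, and because urines not sought in the treatment period cannot be recovered later.

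**What to change.** Reword both exits so that they end study medication only. Seek the weekly urine and TLFB already scheduled, to week 12, from every participant in the modified intention-to-treat sample, whatever ended medication. Flag urines given on methadone, naltrexone or off-study buprenorphine. Report discharges and withdrawals by reason and arm. As a lesser clarification, state the missed-medication trigger as a count, such as two consecutive missed pick-ups; the clinical threshold is for the investigators. Decisions on dosing and referral are unaffected, and the sample size does not change.

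The cost is the $20 visit payment and some existing staff time. Each 10 low-dose discharges after week 1 add 110 visits, or 110 × $20 = $2,200. For the missed-medication rule, two missed days a week as trigger and 10% missed days would mean about 40 of 200 people and 0.0875 × 2,400 = 210 visits, or $4,200. Under the pick-up count, no attending participant is withdrawn and the added cost among attenders is near zero. Attendance after stopping medication will be incomplete, especially among people who have already stopped coming.

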9. SAFTEE
10. SCID for DSM-V for diagnostic clarification of psychiatric and substance use dependence will be completed in an appropriate time period depending on patient's presenting symptoms.
11. Time Line Followback (TLFB)
12. Urine toxicology screening for drugs of abuse (i.e., cannabinoids, opiates, amphetamine, cocaine)
13. Vital signs (blood pressure, heart rate, weight)

The following measures will be completed weekly during study participation. The duration of the weekly assessments will be approximately 45 minutes.

1. Brief Pain Inventory-Short Form
2. Center for Epidemiologic Studies Depression (CES-D) scale Clinical Opiate Withdrawal Scale
3. Columbia-Suicide Severity Rating Scale (C-SSRS)
4. Drug Use Inventory
5. Post Traumatic Stress Disorder Checklist (PCL-C)
6. SAFTEE
7. Time Line Followback (TLFB)
8. Breathalyzer [additional assessment will be done if suspect alcohol use].
9. Urine Toxicology Screening for drugs of abuse (i.e., cannabinoids, opiates, amphetamine, cocaine)
10. Vital signs (blood pressure, heart rate)
11. Weight

The following measures will be completed at 1, 3 and 6 month follow-up:

1. Brief Pain Inventory-Short Form
2. Center for Epidemiologic Studies Depression (CES-D) scale
3. Clinical Opiate Withdrawal Scale
4. Drug Use Inventory
5. Time Line Followback (TLFB)
6. Urine Toxicology Screening for drugs of abuse

For women of childbearing age, a urine pregnancy test will be done at screening, and monthly during study participation.

A. Laboratory Tests and Vital Signs:

- Blood chemistries (chem 19 + GGT, CBC with differential, Thyroid functions, Urinalysis and urine toxicology) and EKG as well as a general physical examination will be performed at intake. Additionally blood chemistries will be taken at week 12.
- Urinalyses: Urines will be analyzed for the presence of drugs of abuse (including opioids, amphetamines, cocaine metabolite and marijuana) on a weekly basis. Breath analysis for alcohol will be performed on a regular basis, although current alcohol physical dependence is among the exclusion criteria.

- Vital signs including blood pressure, heart rate, and weight will be collected each week.
- B. Psychosocial Assessments: A set of instruments will provide general patient information, including demographic data, substance use history, previous substance use and psychiatric treatment history, medical history and family substance abuse history. Assessments include:
 - Brief Pain Inventory – Short Form: BPI-SF is a self-report questionnaire that assesses severity of pain, impact of pain on daily function, location of pain, pain medications and amount of pain relief in the past 24 hours or the past week (Cleeland and Ryan, 1994).
 - Center for Epidemiologic Studies Depression (CES-D) scale: CES-D is a 20-item self-report measure of depressive symptoms. The range of scores is from 0 to 60, higher scores reflecting increased depressive symptoms. The CES-D does not heavily depend on pathological items compared with other scales such as Beck Depression Inventory and does not define clinical depression. The CES-D has been shown to be a reliable and valid scale, and it has been used in several epidemiological studies including cocaine users (Bobo et al., 1998; Orme et al., 1986; Weissman et al., 1977). This measure will be obtained at baseline and weekly thereafter.
 - Clinical Opiate Withdrawal Scale (COWS): Withdrawal signs and symptoms will be assessed using a 22-item withdrawal instrument that has been reliably used to assess opiate withdrawal. This scale rates the following items from 0 to 4: lacrimation, nasal congestion, yawning, sneezing, coughing, throat clearing, restlessness, nausea/vomiting, gooseflesh, sweating, stomach cramps, muscle cramps, and feeling hot/cold. This scale will be used on a weekly basis.
 - Columbia-Suicide Severity Rating Scale (C-SSRS): designed to assess suicidal ideation and suicidal intent.
 - Fagerstrom Nicotine Tolerance Questionnaire (FNTQ): This self-report measure assesses the degree of nicotine dependence and has been used widely in smoking studies (Fagerstrom, 1978). This instrument has demonstrated reliability and validity (Pomerleau et al., 1994; Tate and Schmitz, 1993).
 - Post Traumatic Stress Disorder Checklist (PCL-C): to measure PTSD symptoms. The PCL-C is a self-report scale that shares similar reliability with the CAPS. (Weathers et al. 1996)
 - Structured Clinical Interview for DSM-V (SCID) will be used to obtain DSM-V Opiate use dependence, and other Substance Use Disorder diagnoses. The number of dependence syndrome elements endorsed from the DSM-V criteria will assess severity of opiate and other substance use. This instrument will be administered at baseline or in as timely a manner as patient's condition warrants.
 - Time Line Followback: At intake and weekly thereafter, assessments will be made of opioid and other drug use.
 - Weekly cigarette smoking: At intake and weekly thereafter, self-reports will also be made on cigarette smoking.
- C. SAFTEE: The SAFTEE is a technique for the systematic assessment of side effects in clinical trials. The SAFTEE will be reviewed by the study nurse and specific symptoms, as well as severity, will be recorded. The SAFTEE will be administered weekly.

Data Analysis Methods:

A. Sample Size and Power Analysis:

For this pilot study, we will recruit a total of 200 subjects, 100 subjects in each treatment arm. No previous studies have examined the influence of BUP/NLX dose on treatment outcomes in prescription-opioid dependent individuals. Our sample of 200 will require an effect size of .25 to detect differences between the two treatment groups for the number of opioid positive urines during the treatment period.

B. Statistical analysis:

The principal analyses will be done on the modified intention to treat sample, that is, subjects receiving at least one dose of BUP/NLX. First, we will determine the success of the randomization by comparing the two treatment groups on socio-demographic and baseline clinical characteristics using chi-square for categorical variables and ANOVA for continuous variables. Second, survival analysis will be used to determine differences between experimental groups in treatment retention. Third, random regression analyses (HLM), (Hedeker and Gibbons 1996) will be conducted to examine if the change in opioid use behavior over time varies as a function of the treatment factors.

Risks and Benefits:

Potential risks

1. Buprenorphine: Buprenorphine, formulated as a sublingual tablet, is available alone or in combination tablet containing buprenorphine and naloxone in a ratio of 4:1. The doses of buprenorphine/naloxone used here are within the recommended guidelines of the manufacturer (4-24 mg/day). In this study, combination tablet will be used, since it is less likely to be diverted than the buprenorphine alone formulation. Common side effects of buprenorphine/naloxone include abdominal pain, constipation, nausea, vomiting, headache sweating, sedation, and allergic reaction. Uncommon but more serious adverse effects of buprenorphine/naloxone include hepatic abnormalities, orthostatic hypotension and respiratory depression.
2. Buprenorphine/Naloxone detoxification: Detoxification from buprenorphine/naloxone can produce signs and symptoms of opiate withdrawal, including nasal congestion, abdominal symptoms, anxiety, myalgia, insomnia, sweating, and diarrhea.
3. Blood Drawing: Subjects will have approximately 80 cc of blood drawn as a result of their participation in the study. Blood drawing can cause some pain and may result in bruising and rarely, infection.
4. Nonspecific Risks: Other risks from the counseling, rating scales and urine collections are not beyond usual clinical procedures in a substance abuse treatment program. Confidentiality of these results are specifically protected by Federal laws, and all records will be identified by code number only, with the master file kept under lock by the Principal Investigator or Data Manager.

Risk/Benefit Ratio: This study may help to develop more effective treatment approaches for prescription opioid dependence.

Protection of subjects

- a. Our inclusion and exclusion criteria will be applied by experienced professionals who will be carefully trained and monitored in order to accept only appropriate subjects into the study. Thus, effective screening will exclude subjects who would be placed at an unacceptable risk. This is determined by the medical and psychiatric history, drug use history, the physical

examination, and the laboratory studies done prior to beginning this research protocol (although as stated previously, should a potential participant present already in withdrawal, it will be the decision of the study MD whether or not to randomize the patient prior to laboratory results being available.)

- b. Confidentiality will be protected by having records identified by code number only with the master list including names kept in locked file cabinets in Bldg. 36 . Confidentiality in this study is of the utmost importance to us. All information obtained will be stored in coded form. The paper files will be kept in locked file cabinets in Bldg. 36 and the electronic records will be kept within the VA intranet (M-drive).
- c. Data and Safety Monitoring Plan: The study will be monitored by a Data and Safety Monitoring Board (DSMB). Risks associated with participating in this protocol are moderate. There is adequate surveillance and protection to discover adverse events promptly and keep their effects minimal. The Board will be composed of persons who are experienced in the conduct of clinical trials for the treatment of addictive disorders and who have appropriate expertise in substance abuse and psychopharmacology. There will be at least one physician on the board who is not directly involved in this trial, but who has the requisite expertise. In order for the DSMB to fulfill its mission of assuring the safety of human subjects and the scientific integrity of the study being conducted, the Board will review adverse event data no less than three times per year. During these meetings, the DSMB will review a table of adverse events at these four-month intervals. Following each DSMB meeting, written minutes will be prepared and distributed summarizing any recommendations, including any for interim analyses, as described above. These written reports will insure accurate preparation of any protocol amendments that might be necessary. After each DSMB meeting, this written report will describe all recommendations including additional safety steps. All serious adverse events such as deaths, hospitalizations, and unexpected toxicity will be reported to the IRB as well as our local hospital risk management committee under expedited reporting, i.e., immediately by telephone as the information is available to us, followed by written report within 48 hours. The procedures for written reporting include written documentation using the clinical notes related to the adverse event and specific forms detailing the event with a sign-off by all appropriate supervisory personnel. Communication of recommendations and decisions are made back to the investigator in a timely manner. These reports will also circulate to the DSMB.

Reporting of Adverse Events

An adverse event is any physical or clinical change or disease experienced by the subject at any time during the course of the study, whether or not considered related to the use of the study drug. This includes the onset of new illness and the exacerbation of pre-existing conditions. Subjects will be questioned and / or examined by the investigator or his / her designee for evidence of adverse events. The questioning of subjects with regard to the possible occurrence of adverse events will be generalized such as, "How have you been feeling since your last visit?" The presence or absence of specific adverse events will not be solicited from subjects. All adverse events will be recorded in the subject's medical and / or research records. The onset and end dates, severity, and relationship to the study drug will be recorded for each adverse

event. Any action or outcome (e.g., hospitalization, discontinuation of therapy, etc.) will also be recorded for each adverse event.

All serious adverse events, whether or not deemed drug-related or expected, will be reported by the principal investigator or designee to the IRB within 24 hours (one working day) by telephone. A serious adverse event is any event that: is fatal, is life-threatening (life-threatening is defined as the patient was at immediate risk of death from the AE as it occurred), is significantly or permanently disabling, requires inpatient hospitalization or prolongs hospitalization, is a congenital anomaly or birth defect. Important medical events that may not result in death, be life-threatening, or require hospitalization may be considered a serious adverse drug experience when, based upon appropriate medical judgment, they may jeopardize the patient or subject, and may require medical or surgical intervention to prevent one of the outcomes listed in this definition. Serious adverse events will get reviewed immediately by the PI. Otherwise, this moderate risk study will be monitored quarterly by the PI and the members of the DSMB, and reported to the IRB if trends in AEs emerge.

Informed Consent:

Recruitment will be through VA clinics, word-of-mouth, referrals from area programs and by advertisement. A research staff member will interview individuals that are interested in participating in the study over the phone or in person should a patient present directly to the research staff. If subjects pass the initial screening for the study, they will then come into the clinic for a full screening evaluation. Upon arrival, a research assistant will read the detailed consent form and will ask questions to make sure that the subjects understand the procedure and their rights, and informed consent will be obtained.

Confidentiality: Confidentiality in this study is of the utmost importance to us. All information obtained will be stored in coded form. The names of the subjects will be used in hospital records.

Location of Study: This study will be conducted at the VA Connecticut Healthcare System West Haven campus.

Payment: Subjects will be paid \$30.00 for attending the screening/baseline sessions which includes the 5-day induction period, \$20.00/week for the 12-week treatment period for attending outpatient visits, and \$30.00 for each follow-up visits at 1, 3 and 6 months. Subjects may therefore receive a total of \$360.00 compensation.

Source of Funds: This protocol is being funded by MIRECC.

Duration: The entire study will take approximately four years to complete.

References:

Bobo, J. K., McIlvain, H. E., Leed-Kelly, A., 1998. Depression screening scores during residential drug treatment and risk of drug use after discharge [published erratum appears in Psychiatr Serv 1998 Jun;49(6):828]. *Psychiatr Serv* 49, 693-695.

Centers for Disease Control and Prevention, 2012. CDC grand rounds: prescription drug overdoses - a US epidemic. *MMWR Morb Mortal Weekly Report*, pp. 10-13.

Cleeland, C. S., Ryan, K. M., 1994. Pain assessment: global use of the Brief Pain Inventory. *Ann Acad Med Singapore* 23, 129-138.

Fagerstrom, K. O., 1978. Measuring degree of physical dependence to tobacco smoking with reference to individualization of treatment. *Addict Behav* 3, 235-241.

First, M. B., Spitzer, R. L., Gibbon, M., & Williams, J. B. (2012). *Structured Clinical Interview for DSM-IV® Axis I Disorders (SCID-I), Clinician Version, Administration Booklet*. American Psychiatric Pub.

